Study Protocol and Statistical Analysis Plan

Noise Reduction Preferences in Teenagers and Pre-teens

v.2

March 30 2023

NCT05372094

Protocol Title

Noise Reduction Preferences in Teenagers and Pre-teens

1 Background

The primary goal for pediatric hearing aid fittings is to maximize speech audibility and to mitigate the negative impact of the hearing loss on the child's speech and language development. Research suggests that incidental learning and situational awareness are important for speech and language development. As such, pediatric hearing aids fittings and feature selection can differ from adults. The potentially unique acoustic environments and listening needs of children must be considered when fitting hearing aids. Balancing audibility and comfort by improving SNR with the need for incidental learning has been the challenge for pediatric fittings, and traditionally, such features as directional microphones and noise reduction have been disabled, as these often reduce gain and thereby impact incidental learning, such as which takes place during group work or interactive discussions in the school classroom. However, with developments in noise reduction (as well as directional microphones), the audiology community is becoming aware that these features can benefit children and it should not be assumed that enabling and including such features will negatively impact the child's development and/or learning. In fact, several recent publications have espoused the use of these technologies for children. (McCreery, et al 2012; Stelmachowicz, et al 2010; McCreery, et al 2010; Beck 2008; Beck 2014; Pittman 2011).

Special hearing aid features are typically validated and marketed towards the adult population. As many hearing impaired adults have acquired hearing loss following speech and language development, most hearing aid features are recognized as appropriate and beneficial to adults. However, hearing aids designed and marketed for the pediatric population typically do not include as many features, mainly because such features are not always appropriate for ideal speech, language, and overall learning development.

Dynamic Noise Cancellation and Tap Control are offered in the newest Phonak devices.

This study aims to identify the preferences of older children (teens and pre-teens) for DNC settings when listening in noise, and if personalization of the DNC feature using the app contributes to reduced listening effort. Subjective preference will be evaluated using blinded A/B comparisons and listening effort will be evaluated using both a subjective slider tool (see Picou, et al 2019) and objective methods (accuracy of words correct and verbal response time for monosyllabic words). Additionally, this study will evaluate speech perception at different DNC settings, from off to strong, which will help inform best practices and recommendations for fittings of older children.

2 Objectives

The primary objective for this study is to determine if DNC "on" at a preferred setting reduces the average *self-perceived* listening effort in teens and pre-teens with mild to severe hearing loss, compared to DNC "off".

The secondary objectives are to determine:

-that DNC "on" at a preferred setting is preferred to DNC "off" when listening in loud noise for teens and pre-teens with mild to severe hearing loss.

- that the majority of teens/pre-teens prefer to use Tap Control to access Bluetooth streaming with their smartphones, compared to using HA push button or phone control.
- that speech intelligibility is maintained with DNC “on”

3 Description of the investigational device

The devices used in this investigation are the Audeo Lumity 90 RICs. The myPhonak app will also be used.

For the purposes of this section, the investigational devices will be considered the hearing aid features of Dynamic Noise Cancellation (DNC) and Tap Control, as these are the specific features being studied for this population. These features are found in the Audeo Lumity devices. DNC is a spatial noise canceller which is currently available on the Audeo Lumity 90 and 70 level devices. The DNC setting is done by the HCP within the Target programming software, or by the end-user via the myPhonak app. The options for setting it range from Off, weak (1-9), moderate (10-16) and strong (17-20).

The overall intended purpose of the device is to amplify and transmit sound of the ear and thereby compensate for impaired hearing. Tap Control enables the hearing aid user to control the access to streaming from the hearing aids via taps on the ear instead of using physical controls.

4 Design of the clinical investigation

This investigation is a single-group, single site, interventional study. During the lab testing when participants indicate their preference for listening in noise, and during speech performance testing, they will be blinded as to how the hearing aids are programmed. Participants will serve as their own control as DNC “off” will be a condition in which they are tested.

5 Risks and benefits of the investigational device and clinical investigation

There are minimal risks associated with both the investigational device and participating in the clinical investigation. Identified risks are no greater than those associated with the participants personal hearing aids.

The benefits of participating in the investigation include the possibility of hearing sounds not previously heard, and being able to adjust hearing aids to improve communication in noisy environments. Additionally, participation in this study will help to inform future developments and improvements in hearing device technology for this population.

The research personnel will review these risks with the subjects and answer any questions they have. Hearing aids are not a significant risk investigational device as defined in the FDA 21 CFR 812.3(m).

6 Endpoints

The primary endpoint is listening effort, which is determined by multiple measures from the same dual-task paradigm:

- 1) **Subjective rating** of the task by answering the question “How easy was it to listen?” using a visual analog scale with verbal anchors at the end points such as “It was very easy” to “It was not at all easy”.

Secondary endpoints will include the following:

- 1) **Speech Reception Thresholds** is the lowest level, in dB, in which the participant can correctly repeat key words in a sentence. The adaptive HINT-C test will be used with the noise level presented at 67 dB and the target speech signal at varying levels. SRTs will be obtained with the study devices programmed with four different SPiN programs, each one with a different DNC level. The participant's SRT with their own personal hearing aids at their user settings will serve as the control or baseline.
- 2) **Verbal response time** is the length of time it takes the participant to respond verbally to the monosyllabic words presented in noise, while also performing a visual task simultaneously.
- 3) **Preferences for DNC “on” compared to “off”** will be measured using a forced choice scale A/B comparison. Hearing aids will be programmed with three different SPiN programs, each one with a different DNC setting (off, weak, strong). Participants will be blinded to the settings.
- 4) **Preferences for the use of Tap Control** to access BlueTooth streaming from their smartphone will be measured using a subjective questionnaire which will ask participants to rate which method they prefer: Tap Control, HA push button, or phone control.

7 Inclusion and Exclusion Criteria

Inclusion criteria:

- Children, age 10-17
- Mild, moderate, or moderate-severe binaural sensorineural hearing loss
- Native English speakers with ability to communicate verbally
- Able to read and follow directions
- Access to smartphone and willing to download the myPhonak app to personal smartphone
- Experienced hearing aid users (6+ months)

Exclusion criteria:

- Active middle ear infection
- Unable to follow verbal directions
- Unable to communicate verbally
- Unable to tolerate the physical fit of the device

8 Measurements and procedures

All analyses of the results will occur at the conclusion of the study. Speech scores and subjective questionnaire results will be collected on paper-based forms or electronically through use of a lab-owned tablet. Data from these forms will be entered into an electronic spread-sheet prior to data analysis. It will be stored in a secure Vanderbilt network folder and shared with the Sonova once data analysis is complete on a secure Sonova drive in which only the PI has been granted access.

9 Statistical design and analysis

A power analysis on the primary objective was conducted by the PI using G-Power 3.1. Using an expected effect size for this study of 0.7 (see section 6.3) and assuming a two-condition, repeated

measures study with an alpha level of 5% and a power of 80%, 19 subjects would be necessary. Assuming an attrition rate of 20%, the targeted study enrollment for the primary objective would be 23 participants.

Listening effort will be measured by a self-report, subjective question, "How easy was it to listen?" in each condition (DNC "off" and DNC "on" at preferred setting) which will be asked following a dual-task activity. This consists of a primary task of monosyllabic word recognition and a secondary task of a physical response to a visual probe. For purposes of this study, the accuracy of the word recognition will be calculated as well as the verbal response time. A generalized linear statistical model will be used in which the ratings will be the dependent variable, which will be predicted by response time and DNC condition. If there is a significant effect of the DNC condition and the mean ratings are better for DNC on at a preferred setting, the claim that DNC reduces self-perceived listening effort can be substantiated.

A general linear statistical model will also be used to analyze the secondary endpoint of objective listening effort. The dependent variable will be response time, and the independent variables will be the type of response time (either verbal response time in repeating the word or dual task response time of a button press to a colored shape) and also the DNC setting. Random effects of participant and trial will be evaluated if the data can support the complexity of the random effects. The claim of reduced listening effort can be substantiated if the verbal response time is significantly shorter with DNC on than with DNC off.

One sided binomial tests against 50% will be used to determine if the preference for DNC on is significantly different from the preference for DNC off, for the first lab task of listening to speech in a noisy environment. Preference will be measured via a blinded A/B comparison.

Preferences for the use of Tap Control compared to other methods of accessing Bluetooth streaming will also be analyzed using a binomial test.

Deviations from this statistical plan will be documented in the final study report with justification. Possible reasons for deviation include missing data and/or violated assumptions (e.g., variance, distribution, etc).

10 Investigation Duration

This study is expected to take approximately 6 months, but will depend on the recruitment rate. The expected duration for each participant is approximately 2-4 weeks.

11 Data handling and management

Study data is recorded both with paper and with electronic Case Report Forms (p/eCRF). For each enrolled study participant a CRF is maintained. All CRFs are kept current to reflect the subject's status at each phase during the course of study. Participants cannot be identified in the CRF by name or initials and birth date but an appropriate coded identification is used. All study team members are authorized for the CRF entries and it is assured that any authorized person can be identified both for pCRFs and eCRFs. If pCRFs are used, the investigator's acronym as well as the subject ID is filled in and data are entered into an electronic file for analysis by the respective investigator and data get monitored by the assigned monitor. In case of a self-evident corrections, either the subject does it by himself or the investigator undertakes the correction by crossing out the word/sentence with a single horizontal line and by adding the correction including his personal identifier and the date.

12 Amendments to the CIP

Any necessary amendments to the CIP will be communicated to the study manager/sponsor. A new version of the CIP will be written, with the necessary changes and justification, and the PI will be trained on the amendments. The amended CIP will go through the approval process and necessary signatures obtained from the study manager/sponsor, PI, and statistician. The amended CIP will be uploaded to the eQMS system as an additional revision.

13 Deviations from clinical investigation plan

Deviations from the CIP to protect the rights, safety and well-being of human participants under emergency circumstances may proceed without prior approval of the sponsor and the EC – such deviations will be documented and reported to the sponsor representative (Study Manager) and the EC as soon as possible. Apart from that the investigator is not allowed to deviate from this CIP unless that deviation does not influence the investigation data.

14 Device accountability

The PI or authorized designee keep records documenting the following in a written process:

- Names of participants who received, used, returned, or disposed of device
- Date of receipt, identification, and quantity of each investigational device (batch/serial number or unique code)
- Expiry date (if applicable)
- Date(s) of use
- Participant identification

If a device needs to be replaced due to a device deficiency, the PI will add the new device serial number, date of receipt, and date of return of the defective device on the Device Accountability Log. In the case of a device deficiency, the Adverse Event/Device Deficiency form will be completed by the study manager and PI together.

15 Informed consent process

At the beginning of the first appointment, investigators will hand the consent form to the participant and to participant's legal guardian in a private setting and grant sufficient time to read the whole form. The consent form contains detailed information about incentives and reimbursement. Any questions will be answered and the participant/legal guardian will be given sufficient time to decide whether or not they want to participate in the study. After the participant and legal guardian signs two copies of the consent form, the researcher will sign both copies as well and provide one copy to the participant/legal guardian.

Informed Consent will only be obtained by investigation participants and/or their legal guardians who can provide informed consent themselves before enrollment.

16 Adverse events, adverse device effects and device deficiencies

Device deficiencies and all **adverse events (AE)** including all **serious adverse events (SAE)** are collected, fully investigated and documented in the source document and appropriate case report form (CRF) during the entire investigation period, i.e. from participant's informed con-sent until the last protocol-specific procedure, including a safety follow-up period (ISO-14155, 2020). Documentation includes dates of event, treatment, resolution, assessment of serious-ness and causal relationship to device and/or investigation procedure.

Information on AEs is systematically collected during the regular investigation visits, and phone calls (if applicable).

The following events are to be reported to the Sponsor by the PI (or authorized designee) within 1-2 days after becoming aware of the event:

- Adverse Events
- Serious Adverse Events
- Health hazards that require measures
- Device deficiencies
- Unanticipated Serious Adverse Device Effects

The Sponsor will evaluate SAEs with regard to causality and seriousness. Device deficiencies are also assessed regarding their potential to lead to an SAE (DD with SADE potential).

The following events are to be reported to the Ethics Committee/IRB and to the Competent Authority **within 10 days** by the principal investigator:

- Health hazards that require measures
- Serious Adverse Events

In order to ensure prompt notification, the Sponsor may initially submit an incomplete notifica-tion. The (serious) adverse events will be followed by the PI or Investigator until it has been resolved or until it is recognized as permanent or stable condition. Follow-up may be necessary ac-cording to the study team's medical judgment. In this situation, the follow-up should be docu-mented on the source documents for (serious) adverse events.

17 Vulnerable populations

This investigation includes children age 10-17.

18 Suspension or premature termination of the clinical investigation

The clinical investigation will be suspended or prematurely terminated if the feature and/or investigative device malfunctions or if the participants or researchers are exposed to safety risks other than those outlined in this document. These events may include but are not limited to – natural disaster, widespread outbreak of illness, compromised structure of the investiga-tion site, etc. The trial will be suspended within 5 days of determination that the study or device puts subjects at an unreasonable risk (per 21 CFR 812). The study will be terminated if the participants or researchers are exposed to safety risks other than those outlined in this document.

19 Publication policy

The clinical investigation will be registered in clinicaltrials.gov, a publicly accessible database, as required by U.S. regulations.

The results of the clinical investigation will be published on clinicaltrials.gov no later than one calendar year following the final participant appointment.

An internal report of the results of this investigation will be completed and uploaded to the Sonova Quality Management System.

The results of the clinical investigation will be published in an internal study report. The PI will author a submission to a peer-reviewed journal (publication TBD). The internal study report will be available in eQMS. The PI may present results as well to the stakeholders when study is complete.

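### Verbal response time, a secondary measure, can support an unqualified claim of reduced listening effort even if the primary rating fails, and Section 6 blurs which measure is primary

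*Combined protocol and SAP*

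**What the plan says.** All references are to the combined protocol and SAP.

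- **Section 2, primary objective.** The question is whether DNC at the preferred setting "reduces the average *self-perceived* listening effort in teens and pre-teens", compared with DNC off. The secondary objectives cover DNC preference, Tap Control preference and speech intelligibility. None concerns response time.
- **Section 6, primary endpoint.** "The primary endpoint is listening effort, which is determined by multiple measures from the same dual-task paradigm". One numbered item follows: a rating "of the task by answering the question “How easy was it to listen?” using a visual analog scale".
- **Section 6, secondary endpoints.** Verbal response time is the second item. It "is the length of time it takes the participant to respond verbally to the monosyllabic words presented in noise", while a visual task is also being done.
- **Section 9, sample size.** The calculation is for the primary objective only: effect size 0.7, two repeated conditions, alpha 5%, power 80%, 19 subjects.
- **Section 9, rule for the rating.** "If there is a significant effect of the DNC condition and the mean ratings are better for DNC on at a preferred setting", then "the claim that DNC reduces self-perceived listening effort can be substantiated".
- **Section 9, rule for verbal response time.** The paragraph is introduced as the analysis of objective effort, a secondary endpoint. It ends: "The claim of reduced listening effort can be substantiated if the verbal response time is significantly shorter with DNC on than with DNC off".

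No testing order, gatekeeping, division of alpha or multiplicity adjustment is given. The 5% level appears only in the sample-size calculation.

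**The concern.** Two things do not fit together. First, Section 6 uses a plural for the primary endpoint and then lists a single measure. Second, the two success rules in Section 9 lead to claims of different breadth, and the breadth runs the wrong way. The primary rating earns a claim restricted to self-perceived effort. The secondary verbal time earns a claim about listening effort with no qualifier, and listening effort is the name Section 6 gives to the primary endpoint.

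Since neither rule refers to the other, a trial in which the rating shows nothing could still report, within its own plan, that DNC reduces listening effort. The error rate of that statement is not the one behind the sample size, because there are two chances to reach it.

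**Working it through.** **Step 1: which measure is primary.** Compare the places that bear on it.

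| Place | Rating | Verbal response time |
|---|---|---|
| Section 2, primary objective | yes | no |
| Section 6, numbered under primary | yes | no |
| Section 6, numbered under secondary | no | yes |
| Section 9, sample size | yes, through the primary objective | no |
| Section 9, own success rule | yes | yes |
| Claim that the rule allows | self-perceived effort | reduced listening effort, unqualified |

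The rating is identifiable as primary. The fault lies in the last two rows, together with the plural in Section 6.

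**Step 2: count the routes.** Section 9 also models button-press time, as one type of response time, and calculates word accuracy. Neither has a success rule. There are two explicit routes: the rating and verbal response time.

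**Step 3: reproduce the plan's sample size, to see which sidedness it implies.** Inputs are from Section 9; reading 0.7 as the standardised mean of the paired differences is an assumption. Power comes from the noncentral t distribution with n − 1 degrees of freedom and noncentrality 0.7 × √n.

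- Two-sided 5%: power is 0.799 at n = 18 and 0.823 at n = 19, so 19 are needed. This is the plan's figure.
- One-sided 5%: 15 would be enough.

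The stated 19 therefore implies a two-sided test, although Section 9 does not state the sidedness of the effort tests.

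**Step 4: chance of a false reduced-effort claim when DNC has no effect on either measure.** Both rules require a significant result in the favourable direction, so each two-sided 5% test contributes 2.5%.

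- Rating alone: 0.05 / 2 = 2.5%.
- Either route, independent tests: 1 − (1 − 0.025)² = 4.94%.
- Upper bound at any correlation: 2 × 2.5% = 5%.
- Either route, correlated tests, by simulation of paired t-tests (n = 19, 200,000 runs):

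| Assumed correlation | False favourable claim |
|---|---|
| 0 | 4.9% |
| 0.3 | 4.7% |
| 0.5 | 4.5% |
| 0.7 | 4.2% |
| 0.9 | 3.6% |

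- If each test were one-sided at 5%: rating alone 5%; either route, independent, 1 − (1 − 0.05)² = 9.75%.

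**Limits of the calculation.** The documents give no correlation between the two measures, so a range is shown. The simulation uses simple paired t-tests. The plan's rating model also includes response time as a predictor, and its response-time model includes the type of response; neither feature is represented.

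**The case against.** The strongest reply is that the plan already labels verbal response time as secondary, and that its paragraph opens by speaking of objective effort. In context, the last sentence can be read as a claim about objective effort only. The study aim in Section 1 also names objective methods, verbal response time among them, so the measure belongs to the plan even without a matching objective in Section 2. And under the two-sided tests that 19 subjects imply, the two-route false-claim rate stays below 5%.

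Much of this stands. It makes the matter one of wording and claim scope, not of an unidentifiable primary test. It does not remove the point: the sentence that authorises the claim carries no qualifier, and a success rule should not need its context to limit it. A rate just under 5% is still about double that of the rating alone.

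Three stronger readings are tempting, but the documents do not support them:

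- A reader might infer that any dual-task measure could be presented as primary. The list in Section 6 and the objective in Section 2 contradict that.
- A reader might count three or four routes. Word accuracy and button-press time have no success rule, so an error rate over four measures describes a rule the plan does not contain.
- A reader might quote the chance of any significant result in either direction. Results against DNC cannot trigger either claim.

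**Conclusion.** The point holds in a limited form. The rating is the primary measure, but Section 6 describes the endpoint as plural, and Section 9 lets one secondary measure substantiate the unqualified claim on the construct named as primary, whatever the rating shows.

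Under two-sided testing the excess over the rating alone is about 2 percentage points at an assumed correlation of 0.5 (4.5% against 2.5%) and at most 2.5 points. Only one-sided 5% testing of each measure, which the plan does not state for effort, would take the rate close to 10%. The size thus rests on sidedness and on an assumed correlation. The textual finding, that the trial may claim reduced effort after a failed primary test, rests on neither. The correction is worth making because it is nearly free and changes what the trial may conclude in that case.

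**What to change.** - **Section 6.** Replace the opening sentence with: *The primary endpoint is the subjective rating of listening effort.*
- **Section 9.** Replace the verbal-time rule with a claim limited to *shorter verbal response time with DNC on (secondary, objective measure)*. Add that a claim of reduced listening effort rests on the primary rating.
- **Section 9.** State the sidedness of the effort tests.

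Testing verbal response time only after a significant rating is optional. Once the verbal-time claim is relabelled, it no longer feeds the reduced-effort claim, so the gate is not needed to protect that claim. It would also make an objective result depend on a subjective one.

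The cost is a few sentences. The sponsor gives up an unqualified reduced-effort claim based on verbal response time alone. The primary test and the 19 evaluable subjects stay as they are. By comparison, keeping both measures as full routes with alpha split equally (2.5% each, two-sided) would need 22 evaluable subjects at the same effect size, or would leave power of 0.724 at 19.

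### The SRT control named in section 6 (personal hearing aids) conflicts with section 4 (DNC off) and does not isolate DNC, and section 9 has no SRT analysis to settle it

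*Combined protocol and SAP*

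**What the plan says.** - **Objective (section 2).** One secondary objective is to show "that speech intelligibility is maintained with DNC" on. Unlike the primary and preference objectives, this line does not name its comparator.
- **SRT endpoint (section 6).** "SRTs will be obtained with the study devices programmed with four different SPiN programs, each one with a different DNC level". The levels are not listed. The next sentence says the participant's "SRT with their own personal hearing aids at their user settings will serve as the control or baseline".
- **Design (section 4).** "Participants will serve as their own control as DNC" off is one of the tested conditions. The preceding sentence of that paragraph concerns blinding, and covers speech performance testing as well as preference testing.
- **Settings.** Section 1 says the study will "evaluate speech perception at different DNC settings, from off to strong". Section 3 lists four settings: "The options for setting it range from Off, weak (1-9), moderate (10-16) and strong (17-20".
- **Analysis (section 9).** Analyses are given for the effort ratings, response time, DNC preference and Tap Control preference. None is given for SRT: no contrast, no DNC-on level and no criterion for maintained intelligibility. For the words in the dual task, "the accuracy of the word recognition will be calculated as well as the verbal response time", with no intelligibility analysis attached.

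**The concern.** Section 3 treats the DNC feature, not the whole hearing aid, as the thing under investigation. To show that the feature leaves intelligibility intact, the natural comparison switches only that feature. The control named for SRT switches much more: the device, the fitting, the program and the personal settings. The plan does not standardise those personal settings, so the reference may differ from child to child.

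Two things are at stake. If section 6 is followed as written, the result answers how the study device with DNC on compares with the child's own aids, and could be reported as an answer about DNC. If sections 4 and 6 are both left standing, the reference can be chosen after the SRTs are known, and so can the DNC-on level and the meaning of maintained.

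**Working it through.** **1. Which control applies to SRT?**

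| Place | Control | Specific to SRT? |
|---|---|---|
| Section 4 | DNC off, within participant | No; SRT is not named, but the paragraph covers speech performance testing |
| Section 6 | Personal aids at user settings, as control or baseline | Yes |
| Section 9 | None given | No SRT analysis |

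The endpoint-specific sentence and the design sentence name different references, and the analysis section does not choose between them.

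**2. Is a DNC-off SRT likely to be collected?** Section 6 has four SRT programs with different DNC levels. Section 3 has four settings: off, weak, moderate and strong. Section 1 describes speech perception testing as running from off to strong. The counts and the range agree, so DNC off is evidently one of the four. This is an inference, because section 6 does not list the SRT programs. It does list them for the A/B comparison: "each one with a different DNC setting (off, weak, strong".

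**3. What does the personal-aid contrast estimate?** For one participant, with a higher SRT meaning worse performance:

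(on − personal) = (on − off) + (off − personal)

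The first term on the right is the DNC effect on the study device. The second is the difference between the study device with DNC off and the personal aids. If DNC raises the SRT by L and the study device with DNC off is better than the personal aids by L, the contrast is L − L = 0 and the loss is hidden. If DNC has no effect and the study device is worse by L, the contrast is 0 + L = L and a loss is mimicked. The documents give no value or sign for the second term, so the bias cannot be put in dB.

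**4. How much is left open?** Assuming the four programs in step 2, there are two candidate references and three DNC-on levels: 2 × 3 = 6 single-level contrasts, with none designated.

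**5. What precision would the on-minus-off contrast have?** The plan's figures of 19 evaluable and 23 enrolled concern the primary objective. A two-sided paired t-test at 5% with effect size 0.7 reproduces the 19 (power 0.823; 18 gives 0.799). That calculation does not depend on the SRT control.

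The documents give no SD for SRT, so the unit here is the SD of the paired on-minus-off difference. The 95% CI half-width is t(0.975, n−1)/√n:

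- n = 19: 2.101/√19 = 0.482 SD
- n = 23: 2.074/√23 = 0.432 SD (best case, with no attrition)

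Suppose a non-inferiority margin were set, with the upper limit of the two-sided 95% CI for worsening required to lie below it. With no true loss, 80% power needs the margin m (in SD) that solves P(T > t(0.975, n−1)) = 0.80, where T is noncentral t with n−1 degrees of freedom and noncentrality m√n. This gives m = 0.680 at n = 19 and 0.611 at n = 23. These figures describe the cost of a formal claim. They do not measure the confounding in step 3.

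**The case against.** The strongest reply is that the plan already contains the right control. Section 4 makes DNC off the within-participant control directly after a sentence about speech performance testing, and section 1 includes off among the speech-perception settings. A reader might infer from section 6 alone that DNC off plays no part as a comparator for speech testing, or that the right data will not exist. The documents do not support either reading. What stands is narrower: section 4 never mentions SRT, and the one sentence that does names a different control.

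A second reply is that section 6 says control or baseline. Read as a baseline, the personal-aid SRT is a legitimate descriptive benchmark. This also stands, and the fix keeps it in that role. It does not help if the sentence is applied as a control, which its wording equally allows.

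A third is that the intelligibility objective names no comparator, so maintained could mean relative to what the child hears now. That is a reasonable fitting question, but it concerns the whole device. Because section 3 defines the investigational device as the feature, and the primary and DNC-preference objectives both compare on with off, DNC off is the natural reference here. This remains an inference, and it limits confidence to moderate.

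Word-recognition accuracy from the dual task does not fill the gap. Section 9 only says it will be calculated, and section 1 groups it with the measures of listening effort.

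**Conclusion.** Wrong as written, with moderate confidence. The SRT control in section 6 conflicts with the within-participant control in section 4 and, used as a control, does not isolate DNC. Section 9 does not resolve the conflict. The bias is the off-minus-personal difference; it can go either way and cannot be sized from the documents.

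The conclusion rests on two assumptions: that the intelligibility objective is about the DNC feature, and that the four SRT programs include DNC off.

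A reader might go further and conclude that the intelligibility result is bound to be biased, or that the trial cannot answer the question. The documents do not show that, since the within-device contrast appears to be available and only needs to be named. The point concerns a secondary objective and should be corrected; the primary objective is unaffected.

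**What to change.** **Section 6.** List the DNC levels of the four SRT programs, as is done for the A/B comparison. Name DNC off on the study device as the SRT control. Keep the personal-aid SRT as a descriptive baseline. This also brings section 6 into line with section 4.

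**Section 9.** Add an SRT analysis for the intelligibility objective: the within-participant difference, DNC on minus DNC off, with a two-sided 95% CI. Name the DNC-on level before the data are seen. It can be the same level for every participant, or the program in the category that contains the participant's preferred setting. The second choice needs a stated rule for participants who prefer off. It aligns only approximately with the primary objective, because the categories are wide (weak alone spans 1 to 9). Report the other levels descriptively.

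**Criterion.** Do not read a non-significant difference as maintained intelligibility. Report the estimate and CI descriptively, unless a margin in dB is fixed in advance and the upper limit for worsening is required to lie below it. The documents give no margin or SD to start from, so a margin would need outside justification.

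**Cost.** Section 12 requires a new version of the investigation plan with justification, training of the PI, and signatures from the study manager/sponsor, PI and statistician. A formal claim becomes harder: with no true loss, 80% power needs a margin of at least 0.68 SD at n = 19 or 0.61 SD at n = 23. The descriptive option avoids that requirement but gives up the formal claim. No new test run is expected if DNC off is one of the four programs, and the primary analysis and sample size do not change.
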